#### 9.3.3 Covariates

Not applicable

## 9.4 DATA SOURCES

Data collection will be limited to those available in the medical records of selected patients. All medical records of the 35 included centers will be screened for IPF patients and then patients who initiated treatment with nintedanib since 01 January 2016 up to the end of data collection date will be identified. 5 patients per site will be selected based on a simple randomization of all the patients from each physician.

Demographics and comorbidities will be obtained from the available information of patient's medical records on the date of treatment initiation.

Most of data will be available in the charts but as a routine clinical practice, some data could be missing. However, it will be recorded in the CRF if data for the respective variables was not available. Data will be included in an eCRF by investigators.

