### 9.3.2 Outcomes

#### 9.3.2.1 Primary outcomes

The primary outcome of the study is the distribution of patients across different lung function categories (%FVC and DLCO serving as surrogate markers for IPF severity) of IPF patients at the time of treatment initiation with nintedanib (OFEV®) in routine clinical practice.

As no established severity grading exists, the stratification published by Nathan et al. [9] based on pulmonary function impairment and survival differences will be applied.

Patients will be classified with regards to the FVC and DLCO serving as surrogates for severity:

FVC:

- Mild IPF: FVC > 70% predicted
- Moderate IPF: FVC 50% to 70% predicted (\*)
- Severe IPF: FVC < 50 % predicted

(\*) %FVC has been adapted from 55 to 50% to be aligned with nintedanib (OFEV®) clinical trials program.

DLCO:

- Mild IPF: DLCO >50% predicted
- Moderate IPF: DLCO 35% to 50% predicted
- Severe IPF: DLCO <35% predicted

The study outcomes are defined as follows:

- FVC is the total amount of air exhaled during the lung function test % predicted).
- DLCO is the extent to which oxygen passes from the air sacs of the lungs into the blood (% predicted).

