#### 9.3.2.2 Secondary outcomes

To describe demographic and clinical baseline characteristics of IPF patients at time of treatment initiation with nintedanib (OFEV®).

Descriptive statistics will be provided for the following variables:

- IPF diagnosis: frequency of each method of diagnosis (SLB, HRCT), mean duration of the disease from diagnosis to treatment initiation, frequency of patients with associated emphysema, frequency of patients with UIP pattern (according to international guideline, Raghu et al. 2011)
- At nintedanib (OFEV®) initiation:
  - OFEV® treatment initiation date and frequency of each dose
  - Patient demographics (age, male and female, race)
  - Physical examination ( height, weight, BMI, mean distance of the 6 minutes walking test (6MWT))
  - smoking status (current smokers, former smokers and never smokers)
  - breathlessness grade mMRC [\[10\]](#)
  - concomitant medication (active substance, dose, initiation date, indication)
  - Mean Number and frequency of exacerbations due to IPF in the previous year

To describe comorbidity prevalence at time of treatment initiation: frequency of each comorbidity.

- Comorbidities (Pulmonary infection, Emphysema (combined pulmonary fibrosis and emphysema), Pulmonary hypertension, Lung cancer, Gastroesophageal reflux, Cardiovascular diseases, Hypertension, Dyslipidemia, Diabetes mellitus, Obstructive sleep apnoea, Other)

To describe the distribution of patients across different lung function categories based on reimbursement threshold (FVC >80%, 50-80%, and <50%)

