## 9.5 STUDY SIZE

The following table illustrates the precision of estimates of the prevalence of a specific lung function profile within the population of interest depending on the observed rate of affected patients and the sample size. The dropout rate is assumed to be 10% for all scenarios.

Precision is estimated based on two-sided 95% confidence intervals.

Table 1 Precision table

N	N to be analyzed	% observed in subsample	95% CI	Precision
100	90	7.8% (7 out of 90)	[2.2; 13.3]	±5.6
150	135	8.1% (11 out of 135)	[3.5; 12.8]	±4.7
175	158	8.2% (13 out of 158)	[3.9;12.5]	±4.3
100	90	50.0% (45 out of 90)	[39.7; 60.3]	±11.3
150	135	50.4% (68 out of 135)	[41.9; 58.8]	±8.5
175	158	50.0% (79 out of 158)	[42.2;57.8]	±7.8

It can be seen that by raising the sample size from 100 to 150 patients, precision improves to less than  $\pm 5\%$  for the small sample of 8% and to less than 10% for the large sample of 50%. Precision can be further improved to less than  $\pm 4.5\%$  for the small proportion of 8% and to less than 8% for the large sample of 50% if 175 patients will be recruited.

Planning a recruitment of 175 patients allows for an acceptable precision of prevalence of a specific lung function profile (see section 9.3.2.1) estimates.

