## 9.7 DATA ANALYSIS

The proposed methods for statistical analysis presented below are a summary of the methods that will be applied in the study to analyse the data collected and to answer the study objectives. Missing data will not be imputed in the main analysis (but eventually in sensitivity analyses as deemed appropriate). When applicable, the presence of potential outliers will be indicated. Analysis will primarily be performed including these outliers. However, excluding the respective patients in sensitivity analyses might be a reasonable approach to assess the impact of these outliers.

Analyses will be performed by the CRO . Since the study is essentially descriptive the variables included in the study objectives will be analysed with measures of central tendency (mean and median), variability/dispersion (standard deviation and

interquartile ranges), absolute and relative frequencies, and ranges. 95% confidence intervals will be provided as appropriate.

Missing values and data not available in the charts will be displayed in separate categories.

All the analyses will be performed using the Statistical Package for the Social Sciences (SPSS), version 22.

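### The plan cannot tell inability to perform DLCO from a value simply absent from the chart, so disease-related absence would understate the severe DLCO share by an unknown amount

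*Combined protocol and SAP*

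**What the plan says.** The primary outcome (section 9.3.2.1) is the distribution of patients over FVC classes and, separately, over DLCO classes. Each class is a range of per cent predicted; the worst DLCO class reads "Severe IPF: DLCO <35% predicted". There is no class for a patient who could not do the test.

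On absent values, section 9.4 warns that some data may be missing and adds that "it will be recorded in the CRF if data for the respective variables was not available". Section 9.7 rules out imputation in the main analysis, leaves it optional and unspecified for sensitivity analyses, and says "Missing values and data not available in the charts will be displayed in separate categories". Section 9.7.1 promises percentages of all patients and of patients with data for qualitative variables under the secondary objectives. For the primary objective it promises frequencies and names no denominator. Section 9.9 accepts that missing values may weaken the conclusions but does not connect them with severity.

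The six-minute walk test (6MWT) appears among the secondary outcomes (section 9.3.2.2) as a mean distance and defines no severity class.

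On size, section 9.5 states "The dropout rate is assumed to be 10% for all scenarios" and "Planning a recruitment of 175 patients allows for an acceptable precision of prevalence of a specific lung function profile".

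**The concern.** The severe share matters in this study. Section 7 records that the pivotal trials excluded patients below 50% FVC or 30% DLCO, and section 9.3.1 notes that the label covers all levels of lung function. How far routine use reaches into severe disease is what the primary table is meant to show.

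A class that can be entered only with a number loses every patient without one. Section 7 describes IPF as a disease of dyspnoea and reduced gas transfer. It is a fair inference from what the tests demand, though not a figure in the documents, that advanced disease can itself be the reason why a DLCO or walk test was not completed. If so, a chart note that the patient could not perform DLCO is information about severity, and the plan as described does not keep it apart from a test never requested or a report never filed.

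Neither denominator repairs this. A percentage of patients with data drops the unable patient; a percentage of all patients counts that patient as not severe.

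**Working it through.** **Inputs.** All from section 9.5 unless marked.

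- Planned 175, analysed 158 after 10% loss: 175 × 0.9 = 157.5, rounded to 158, so 175 − 158 = 17 not analysed.
- Example small proportion 13/158, with interval 3.9 to 12.5 and precision ±4.3.
- Interval type: "Precision is estimated based on two-sided 95% confidence intervals".
- Assumption A: the example rate stands in for the severe DLCO share. The plan does not label it so.
- Assumption B: the 17 are patients without a DLCO value. The plan calls them dropout; section 9.11.1 marks withdrawal as not applicable, which makes this reading plausible but not stated.
- Unknown: f, the fraction of the 17 who are truly severe. It is varied from 0 to 100%.

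**Step 1. The plan's own figure.** With p = 13/158 = 8.23%, the Wald half-width is 1.96 × √(p(1 − p)/158) = 4.28 points, giving 3.94 to 12.51. The stated 8.2% [3.9; 12.5] ±4.3 is reproduced.

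**Step 2. What would be reported.** Among patients with data: 13/158 = 8.2%. Among all patients: 13/175 = 7.4%.

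**Step 3. What could be true.** True share = (13 + 17f)/175.

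| f | True severe share | Minus the 8.2% reported among patients with data |
|---|---|---|
| 0% | 7.4% | −0.8 |
| 8.2% | 8.2% | 0.0 |
| 25% | 9.9% | +1.6 |
| 50% | 12.3% | +4.1 |
| 75% | 14.7% | +6.5 |
| 100% | 30/175 = 17.1% | +8.9 |

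The with-data percentage is understated only when f exceeds 8.2% and is overstated below that. The all-patients percentage is understated as soon as one absent patient is severe.

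**Step 4. Compare with the planned precision.** The range from missing data alone is 17/175 = 9.7 points wide. The full width of the stated interval is 2 × 4.3 = 8.6 points. Nine of the 17 must be severe before the shift passes the half-width: 22/175 = 12.57%, which is 4.34 points above 8.23%. Eight give 21/175 = 12.0%, a shift of 3.8 points.

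**Step 5. What a reason code would add.** If u of the 17 were documented as unable, the share *severe or unable* would be (13 + u)/(158 + u):

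- u = 0: 8.2%
- u = 4: 17/162 = 10.5%
- u = 8: 21/166 = 12.7%
- u = 17: 30/175 = 17.1%

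This is a composite. It equals the severe share only if every unable patient would have scored below 35%. Its value is that u is observed, whereas f is not.

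**The case against.** The best reply is that the protocol is silent rather than wrong. The eCRF is not in the documents, the Data Management Plan was still to be written (section 9.6), and Annex 1 lists the SAP as a stand-alone document. Any of these could carry a reason code. The promise in section 9.7 of separate categories can even be read as already dividing two kinds of absence. This stands as a caution. It is not a full answer: the protocol's own checklist (item 10.5) points to section 9.7 as the place where missing-data handling is described, and nothing there, nor in section 9.4, mentions a reason. No routine source data verification is planned (section 9.8), so a reason not captured at extraction is unlikely to be recovered later.

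The reply also correctly blocks four stronger conclusions that a reader might draw:

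- *That the severe share is understated outright.* Tests not requested or not filed may belong to patients with mild disease, and the documents say nothing about how many patients were unable or how ill they were.
- *That 8.2% is the plan's expected severe share.* It is an illustrative rate, set beside a 50% scenario, and is tied to neither DLCO nor severity.
- *That missing walk tests remove patients from the severe class.* No class uses the 6MWT. Selective absence could only bias the mean distance, probably upwards.
- *That the bias could not be bounded afterwards.* The count of absent values will be recorded and displayed, so a worst case can be computed. FVC is graded separately and breathlessness grade is collected, so patients without DLCO can be partly described.

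**Conclusion.** The point holds in a limited form. As described, the plan does not separate inability to perform DLCO because of respiratory status from other absence, and patients with documented inability fall outside the graded DLCO classes. To the extent that absence is caused by the disease, the severe DLCO share is understated; the net direction over all absent values cannot be settled from the documents.

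Under assumptions A and B, the true share lies between 7.4% and 17.1%. The display of missing values therefore allows a bound, but one wider than the plan's own confidence interval. At most the with-data percentage is 8.9 points too low, about twice the stated precision. That needs all 17 to be severe, and the shift stays within ±4.3 unless at least nine are.

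This is an inexpensive improvement to make before data collection, not a flaw that invalidates the primary table.

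**What to change.** In the eCRF, add a reason for absence for DLCO, and likewise for FVC and 6MWT, with five options:

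1. unable because of respiratory status, as stated in the chart
2. contraindicated for another reason
3. not requested
4. done but result not found
5. unknown

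Keeping option 2 apart from option 1 avoids counting unrelated contraindications alongside severe disease.

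In sections 9.3.2.1 and 9.7.1, show option 1 as its own row beside the graded classes. Report the severe share among measured values and, as a prespecified sensitivity analysis, the share *severe or unable*, with the denominator of each written out. Report 6MWT distance among those tested together with the number unable.

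The cost is one drop-down per test, one table row and one additional percentage, all of which can be in place before the planned start of data collection on 01 September 2017. The downside is that some charts will not give a reason and will stay as unknown, so the uncertainty will narrow but may not disappear.

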## 9.5 STUDY SIZE

The following table illustrates the precision of estimates of the prevalence of a specific lung function profile within the population of interest depending on the observed rate of affected patients and the sample size. The dropout rate is assumed to be 10% for all scenarios.

Precision is estimated based on two-sided 95% confidence intervals.

Table 1 Precision table

N	N to be analyzed	% observed in subsample	95% CI	Precision
100	90	7.8% (7 out of 90)	[2.2; 13.3]	±5.6
150	135	8.1% (11 out of 135)	[3.5; 12.8]	±4.7
175	158	8.2% (13 out of 158)	[3.9;12.5]	±4.3
100	90	50.0% (45 out of 90)	[39.7; 60.3]	±11.3
150	135	50.4% (68 out of 135)	[41.9; 58.8]	±8.5
175	158	50.0% (79 out of 158)	[42.2;57.8]	±7.8

It can be seen that by raising the sample size from 100 to 150 patients, precision improves to less than  $\pm 5\%$  for the small sample of 8% and to less than 10% for the large sample of 50%. Precision can be further improved to less than  $\pm 4.5\%$  for the small proportion of 8% and to less than 8% for the large sample of 50% if 175 patients will be recruited.

Planning a recruitment of 175 patients allows for an acceptable precision of prevalence of a specific lung function profile (see section 9.3.2.1) estimates.

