Protocol date: 11 May 2017	Study number: 1199-0295	Version/Revision: 1.0	Version/Revision date: Not applicable

- Severe IPF: DLCO <35% predicted
 
The secondary objectives are:
 
 
○ To describe demographic and clinical baseline characteristics of IPF patients at time of treatment initiation with nintedanib (OFEV®)
 
○ To describe comorbidity prevalence at time of treatment initiation
 
○ To describe the distribution of patients across different lung function categories based on reimbursement threshold (FVC>80%, 50-80%, and <50%)
 
			
Study design:	
Non-interventional study based on medical charts of multiple centers, of IPF patients treated with nintedanib (OFEV®). Patients will be characterized at time of treatment initiation (cross-sectional design).
 
IPF patients with a confirmed diagnosis of IPF, who initiated treatment with nintedanib from 01 January 2016, will be selected.
		
Population:	
Approximately 35 Pulmonology Services of Hospitals in Spain will be the basis for the study. The sites will be distributed across whole Spain and will be selected according to previous experience in clinical trials, named-patient program and access to nintedanib (OFEV®).
 
The participating investigators will review all medical records of their IPF patient's since 01 January 2016 and select all patients who initiated treatment with nintedanib (OFEV®) in the study period.
		
Variables:	
All variables will be obtained from medical records:
 
 
- IPF diagnosis: method of diagnosis, date of diagnosis, , UIP pattern
 
- At nintedanib (OFEV®) initiation: 
 
- OFEV® treatment initiation date and dose
 
- Patient demographics (age, sex, race)
 
- Physical examination (height, weight, BMI, 6 minutes walking test (6MWT))
 
- Smoking status
 
- Breathlessness grade
 
- Pulmonary function: %FVC, %DLCO
 
- Comorbidities
 
- Concomitant medication
 
- Previous IPF treatment with pirfenidone, if any: initiation date,
 
 
 
		

Name of company: Boehringer Ingelheim																																							
Name of finished medicinal product: OFEV®																																							

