### 9.3.1 Exposures

Patients in this study will have been prescribed nintedanib (OFEV®) treatment for their IPF on or after 01 January 2016. Prescription of the treatment will have been done under the sole responsibility of the healthcare professional. The date of treatment initiation and the dose will be assessed.

In Spain, nintedanib (OFEV®) is on the market since December 2015, however, in some regions of the country, nintedanib is only reimbursed in a limited type of IPF patients (for example, with a %FVC between 50% and 80% or just >50%), although the indication of local label include all type of IPF patients, independent of their pulmonary function.

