#### **9.7.1 Main analysis**

For the primary objective absolute and relative frequencies of patients across different lung function categories will be calculated.

For the secondary objectives:

To describe demographic and clinical baseline characteristics of IPF patients at time of treatment initiation with nintedanib (OFEV®) and prevalence of comorbidities, descriptive statistics and confidence interval at 95% will be calculated for the key variables defined. For the quantitative variables the number of evaluable patients and the measures of central tendency and dispersion (median, the standard deviation, the median, Q1 and Q3) will be obtained, and for the qualitative variables the absolute and relative frequencies relative to the total of patients and to the total of patients with data (total percentage and valid percentage, respectively) will be obtained.

For the secondary objective to describe the distribution of patients based on reimbursement threshold, absolute and relative frequencies of patients across different lung function categories will be calculated.

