## **9.12 BIAS**

In order to ensure representativeness of patients among the whole country, each Investigator will include 5 patients. To minimize selection bias, a simple randomization will be applied. The Investigator will share an anonymized list of all of patients who meet selection criteria with the CRO. The list will include the minimum patient data to be identifiable by the investigator, for example, age, gender and treatment initiation date. Then, CRO will generate a random sequence of the 5 patients to be included and will inform the Investigator.

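### The precision stated for 175 patients assumes independent patients, although five are drawn from each of about 35 sites; the statements should be made conditional

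*Combined protocol and SAP*

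**What the plan says.** Table 1 in section 9.5, repeated in the abstract, gives ±4.3 points for 13 of 158 patients and ±7.8 points for 79 of 158. The 158 are 175 recruited less 10% dropout. The text then says, without any condition, that precision falls below ±4.5 points at 8% "and to less than 8% for the large sample of 50% if 175 patients will be recruited", and calls this acceptable.

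On sampling, section 9.4 says "5 patients per site will be selected based on a simple randomization of all the patients from each physician". Section 9.12 gives the purpose: "In order to ensure representativeness of patients among the whole country, each Investigator will include 5 patients". Section 9.11 plans 175 patients from 35 services. The abstract adds: "The sites will be distributed across whole Spain". Section 9.3.1 notes that "in some regions of the country, nintedanib is only reimbursed in a limited type of IPF patients", with limits defined by %FVC.

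On analysis, section 9.7.1 says "For the primary objective absolute and relative frequencies of patients across different lung function categories will be calculated". For baseline characteristics and comorbidities, "descriptive statistics and confidence interval at 95% will be calculated for the key variables defined". A confidence interval for the lung function categories therefore rests on the general sentence in section 9.7: "95% confidence intervals will be provided as appropriate". Neither section names an interval method. Section 9.7 describes itself as a summary, and Annex 1 lists a separate SAP that is not among the documents.

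**The concern.** Five patients from each site form a two-stage sample. Random selection within a site guards against picking favourable cases there, but it does not remove differences between sites. When results are meant to describe the country and not just these 35 services, between-site variation belongs in the variance. The precision figures leave it out and do not say so.

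Two things are at stake. The sample size justification may promise more precision than the study delivers, and its margins are thin: 7.80 against a limit of 8, and 4.28 against 4.5. Any 95% confidence intervals computed as if patients were independent may also be somewhat too narrow.

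**Working it through.** **Inputs from the documents:** 158 analysed of 175; 13/158 and 79/158; two-sided 95% intervals; about 35 sites with 5 patients each. **Assumed:** the ICC, shown from 0 to 0.10.

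**1. Reproduce Table 1.** Half-width = 1.96 × √(p(1−p)/n).
- 79/158: 1.96 × √(0.25/158) = 7.80 points, interval 42.2 to 57.8. This matches.
- 13/158: 1.96 × √(0.0823 × 0.9177/158) = 4.28 points, interval 3.9 to 12.5. This matches.

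Other forms do not fit. A continuity correction gives ±8.11 and ±4.60. Wilson gives 42.3 to 57.7 and 4.9 to 13.6. Clopper-Pearson gives 41.95 to 58.05 and 4.45 to 13.66. The printed figures are therefore Wald intervals for independent patients.

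**2. Allow for site.** Mean analysed patients per site: m = 158/35 = 4.514. Design effect: DE = 1 + (m − 1) × ICC = 1 + 3.514 × ICC. The half-width is multiplied by √DE. An interval using the t quantile on 35 − 1 = 34 degrees of freedom (2.032 in place of 1.96) is about 4% wider again.

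| Assumed ICC | DE | Effective n | ± at 50%, z | ± at 8.2%, z | ± at 50%, t | ± at 8.2%, t |
|---|---|---|---|---|---|---|
| 0 | 1.000 | 158.0 | 7.80 | 4.28 | 8.1 | 4.4 |
| 0.01 | 1.035 | 152.6 | 7.93 | 4.36 | 8.2 | 4.5 |
| 0.02 | 1.070 | 147.6 | 8.07 | 4.43 | 8.4 | 4.6 |
| 0.05 | 1.176 | 134.4 | 8.45 | 4.65 | 8.8 | 4.8 |
| 0.10 | 1.351 | 116.9 | 9.06 | 4.98 | 9.4 | 5.2 |

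**3. Break-even ICC (z-based).**
- 8-point limit at 50%: ((8/7.796)² − 1)/3.514 = 0.015.
- 4.5-point limit at 8.2%: ((4.5/4.285)² − 1)/3.514 = 0.029. At exactly 8.0% the base half-width is 4.230 and the break-even is 0.037.

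With m = 5 in place of 4.5, the first two become 0.013 and 0.026.

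**4. Does the choice of 175 over 150 change?** Unadjusted, 68/135 gives ±8.43 against ±7.80, a gain of 0.6 points. At ICC 0.05, 135 analysed patients give ±9.02 with 35 sites (DE 1.143) or ±9.14 with 30 sites (DE 1.175), against ±8.45 for 158. The gain is 0.6 to 0.7 points, so the comparison is unaffected.

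**5. Coverage of nominal 95% intervals at 50%.** Beta-binomial simulation, 60,000 runs, 18 sites of five and 17 of four. Site-clustered means Taylor linearisation with t on 34 degrees of freedom.

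| ICC | Unadjusted Wald | Site-clustered |
|---|---|---|
| 0 | 95.4% | 95.0% |
| 0.05 | 93.2% | 94.9% |
| 0.10 | 91.2% | 94.9% |

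**6. If patients are alike only by region.** Assume seven regions of five sites, all represented, at 50% (40,000 runs). At regional ICC 0.05 / 0.10 the unadjusted interval covers 95.3% / 95.6%, the site-clustered one 96.8% / 97.9%, and the site-clustered one with region as a stratum 95.0% / 94.9%.

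**The case against.** **No ICC is documented.** Every loss of precision above is assumed. That stands. A reader might infer that the two statements are false or that the study is too small. The documents do not support either reading: the statements hold at a small enough ICC, and Table 1 illustrates precision and sets no target.

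**The only documented source of similarity is regional and concerns FVC.** A reader might infer that the reimbursement limits show clustering by site. They act by region, and the sites are spread over Spain. If that is the whole mechanism and all regions are covered, step 6 shows the unadjusted interval to be adequate and a plain site-clustered one too wide. Nothing comparable is described for DLCO or comorbidities. This stands, and it is why region is offered as a stratum.

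**The study is descriptive and the SAP is unseen.** A reader might infer that the primary analysis will report wrong intervals. Section 9.7.1 promises only frequencies for the lung function categories, and the stand-alone SAP may already adjust for site, so the missing interval method cannot be held against the plan. Neither point rescues section 9.5, which justifies the study size by interval width without a condition.

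**Sites were not sampled at random.** They are chosen for trial experience, named-patient use and access to the drug, so a cluster variance treats them as exchangeable when they may not be. This stands as a limit of any adjustment. If inference is confined to these sites, the between-site component drops out; the national aim in section 9.12 points the other way.

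**A t-based interval exceeds 8 points even at ICC 0** (±8.1), so z-based planning figures would not match the intervals reported. This is correct, and the two kinds of figure must be labelled.

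**Conclusion.** The point holds as an unstated assumption, not as an error of arithmetic. Both statements are right for independent patients and conditional for the sample as designed. The first fails above an ICC of about 0.015 and the second above about 0.029. Over an assumed ICC of 0.01 to 0.10 the loss is about 0.1 to 1.3 points at 50% and 0.1 to 0.7 points at 8.2%. Unadjusted intervals at 50% would cover about 93% at ICC 0.05 and 91% at 0.10, where sites themselves differ.

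This rests on an assumed ICC, on inference to patients beyond these sites, and on about 4.5 analysed patients per site. The effect is modest, and 175 remains a defensible number. The change is worth making because it is cheap; confidence is medium.

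**What to change.** Keep 175 patients.

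- **Section 9.5 and abstract:** state that Table 1 and both precision statements assume independent patients. Add illustrative half-widths for an assumed ICC of 0.01 to 0.10: ±7.9 to ±9.1 at 50% and ±4.4 to ±5.0 at 8.2%. Label them z-based, and note that a site-clustered interval with t on 34 degrees of freedom is about 4% wider (±8.1 and ±4.4 at ICC 0; ±8.2 to ±9.4 and ±4.5 to ±5.2 over ICC 0.01 to 0.10).
- **Section 9.7:** where a 95% confidence interval for a proportion is reported, compute it with site as the cluster, adding region as a stratum if sites are chosen by region. Alternatively, report that interval as a sensitivity analysis beside the unadjusted one.
- **Section 9.9:** note that this does not correct for the non-random choice of sites.

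The interval form for small proportions is a separate matter for the SAP: at 8%, simulated Wald coverage is only 93.4% even at ICC 0.

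Cost: a few sentences and one variance calculation from site totals, with no added patients or data. The stated precision looks less favourable and intervals widen slightly. At 50% the mean half-width is about ±8.0 instead of ±7.8 if the ICC is 0. Intervals are wider than needed if similarity is only regional and region is not used as a stratum.
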